## Study Protocol

The process of insufflation will be used on all laparoscopic gynecological surgical patients and for the research protocol the amount of carbon dioxide measuring 12 mmHg used for the experimental group B is less than the standard amount of 15 mmHg used for the control group A. Insufflation pressures of either 12 mmHg (group B) or 15 mmHg (group A) will be used for this research, regardless of the subject's BMI, however it is noted that for patients with extreme upper BMIs, visualization can be more challenging. BMI will be one of the data points recorded for patients, however the randomization of the subjects to 12 mmHg (group B) or 15 mmHg (group A) will not be dependent on their BMI. Our maximum BMI for inclusion of subjects will be a BMI of 55.0.

Procedures other than Treatments:

### Visit 1 (Day 0)

- Give informed consent at routine doctor visit (this will take an additional 30-45 min) – for research purposes only
- Information such as your age, weight, height, and medical history such as [previous heart attacks, etc.] will be copied from your medical record. Specifically, the following items will be collected: age, race, ethnicity, insurance status (public vs. private), body mass index (BMI), additional medical health conditions, surgical history-prior abdominal surgery, history of chronic pain, history of prior chronic opioid use, pre-operative medications – opioid/analgesic, history of alcohol and tobacco use, history of depression/anxiety; (this will take an additional 30-45 min) – for standard of care and for research purposes;

### Visit 2 (Day 1)

- Post-anesthesia randomization to group A or group B, (this will take an additional 5-10 min) – for research purposes only;
- Intra-operative insufflation using 15 mmHg (standard-group A) or 12 mmHg (experimental-group B), adjustment of intra-operative insufflation pressure; (this will take an additional 5 min-10 min) – insufflation for group A is done as standard of care; insufflation for group B is done for research purposes only;
- Post-operative assessment to include the procedure details: indication for procedure, length, estimated blood loss, surgical complications, estimated blood loss, pathology, visual analog scale (VAS), pain medication – prescribed and taken, length of hospital stay, (this will take an additional 30-45 min) – for standard care and for research purposes;

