### **Statistical Analysis Plan**

We have estimated a necessary sample size of 50 participants per group (100 total) with an anticipated effect size of 0.54 based on estimated means of 17mm for the experimental arm (SD 20mm) and 29mm for the control arm (SD 24mm), accounting for expected loss to follow up of 10%. Patients were randomized using 10 block groups of size 10 each.

We will provide a table of demographic and clinical characteristics by assigned group. For continuous variables, we will provide means and standard deviations per group, applying a t-test for comparison of independent means. For categorical variables, we will provide counts and percentages, applying chi-square test for comparison of proportions.

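### No pre-operative VAS is listed and no adjustment for baseline pain is planned, which costs precision but does not bias the comparison of pressures

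*Combined protocol and SAP*

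**What the plan says.** **Visit 2 (Day 1)** contains the only VAS in the documents. The item begins "Post-operative assessment to include the procedure details: indication for procedure, length, estimated blood loss, surgical complications" and later lists "visual analog scale (VAS), pain medication – prescribed and taken, length of hospital stay". The same visit includes "Post-anesthesia randomization to group A or group B", so any reading taken before anaesthesia would also come before allocation.

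**Visit 1 (Day 0)** lists no pain score. It does record "history of chronic pain, history of prior chronic opioid use, pre-operative medications – opioid/analgesic", with other medical history, partly by copying from the medical record.

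**Study Protocol** gives one eligibility limit in the text available: "Our maximum BMI for inclusion of subjects will be a BMI of 55.0". No exclusion for chronic pain appears there.

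**Statistical Analysis Plan** sizes the trial at 50 per group on assumed means of 17 mm (SD 20) and 29 mm (SD 24), an effect size of 0.54 and 10% loss to follow-up. It does not name the outcome, but values in millimetres point to the VAS. It mentions blocks of 10 and no stratification factor: "Patients were randomized using 10 block groups of size 10 each". Continuous variables are compared by t-test and categorical variables by chi-square test. No covariate is named.

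**The concern.** Patients with a history of chronic pain or opioid use can enter the trial, as far as the available text shows. Their pain before surgery will contribute to their score afterwards. That contribution has nothing to do with insufflation pressure, and in an unadjusted t-test it sits in the within-arm standard deviation.

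A score taken before surgery on the same scale would let the analysis remove the part of that variation it predicts, and would let the baseline table show pain by arm in the units of the outcome. The plan has neither the score nor an adjustment for the related history it does collect. At stake are the width of the confidence interval and the chance of detecting the 12 mm difference the trial was sized for.

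**Working it through.** **Inputs from the Statistical Analysis Plan.** Means 17 and 29 mm, SDs 20 and 24 mm, 50 per group, 10% loss. Evaluable per arm: 50 × 0.90 = 45.

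**Inputs assumed.** Alpha, sidedness and power are not stated; the main calculation takes alpha 0.05 two-sided. The correlation r between pre- and post-operative VAS is not given; the range 0.2 to 0.5 is used, equal in both arms.

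**Step 1: the plan's own figures.** Pooled SD = sqrt((20² + 24²)/2) = sqrt(488) = 22.09 mm. Effect size = 12/22.09 = 0.543, matching the stated 0.54. The 50 per group is approached only with a one-sided 5% t-test at 80% power: 43 or 44 per group, which after division by 0.90 becomes 48 or 49. The two-sided t-test at 80% power needs 55, which becomes 62.

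**Step 2: effect of a baseline covariate.** ANCOVA leaves a residual variance of (1 − r²) times the unadjusted variance. So:

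- SD after adjustment = 22.09 × sqrt(1 − r²)
- SE of the arm difference = that SD × sqrt(2/45)
- Power = Φ(12/SE − 1.96)

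| r | Variance removed | SD (mm) | SE (mm) | Power, 45 per arm | N per arm for 80% power, with 10% loss |
|---|---|---|---|---|---|
| no covariate | 0% | 22.09 | 4.66 | 73.1% | 60 |
| 0.2 | 4% | 21.64 | 4.56 | 74.9% | 58 |
| 0.3 | 9% | 21.07 | 4.44 | 77.1% | 55 |
| 0.4 | 16% | 20.25 | 4.27 | 80.3% | 50 |
| 0.5 | 25% | 19.13 | 4.03 | 84.5% | 45 |

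These use the normal approximation; the exact t-test without a covariate has 72.2% power. Estimating the slope inflates the variance by about 1/(90 − 4) = 1.2%, which takes a noticeable share of the 4% gain at r = 0.2 and little of the gain at r = 0.5.

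With a one-sided 5% test (1.645 in place of 1.96), power is 82.4% without the covariate, 83.8% at r = 0.2 and 90.8% at r = 0.5.

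**Step 3: is the unadjusted comparison biased?** In 10,000 simulated trials per scenario, with 45 per arm, a true difference of 12 mm and total SD 22.09, chronic pain was given to an assumed 20% or 30% of patients (adding 15 mm) or 40% (adding 20 mm). The unadjusted difference averaged 11.9 to 12.0 mm, and two-sided type I error was 4.8% to 5.4%. There is no bias and no inflation.

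**Step 4: what the recorded history can recover.** In the same simulations, adjusting for chronic-pain history alone raised power from 72% to 75%, 77% and 81% in the three scenarios.

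**The case against.** The strongest reply is that randomisation already deals with pre-existing pain. It is fixed before allocation, so it is balanced in expectation, and chance imbalance is already counted in the standard error and the p-value. Step 3 bears this out, and the reply stands.

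A reader might infer that, without a baseline score, pre-existing pain cannot be separated from the effect of pressure. The documents do not support that: allocation is randomised, so the arm difference estimates the effect of assigned pressure with or without a baseline. Nor does the t-test treat patients as having equal starting pain; differences between patients are part of the SDs of 20 and 24 mm.

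Chance imbalance is also easily overstated. If pre-operative VAS had SD 25 mm (assumed), the slope on the outcome would be r × 22.09/25, or 0.27 to 0.44 for r of 0.3 to 0.5. A 5 mm imbalance would then move the post-operative difference by 1.3 to 2.2 mm, against the planned 12 mm.

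Two further replies stand in part. The gain rests on an assumed correlation and is small at 0.2. And Visit 1 already collects pain history, opioid use and analgesics, so arms can be compared on those and some precision recovered. But no adjustment for them is planned, and they do not give current pain on the outcome's scale.

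Finally, the past tense in "Patients were randomized using 10 block groups of size 10 each" suggests that enrolment may have started or finished, although other parts of the same section are in the future tense. A new reading may be possible for only some patients, or for none.

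**Conclusion.** The point holds as one of efficiency. No pre-operative VAS is listed and no adjustment for baseline pain is planned, so the trial gives up precision it could have at little cost. The unadjusted comparison remains valid.

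For r between 0.2 and 0.5 the loss is 4% to 25% of the residual variance, or about 2 to 11 percentage points of power at two-sided 5% (74.9 − 73.1 = 1.8; 84.5 − 73.1 = 11.4). At r = 0.4 the covariate would bring the two-sided requirement for 80% power from 60 down to the planned 50 per arm; at r = 0.2 the gain is marginal.

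This rests on the assumed correlation, the assumed alpha and sidedness, the plan's own SDs, and the reading that the sample-size outcome is the VAS. The absence of a baseline score and of planned adjustment rests on the text alone.

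**What to change.** **For patients not yet operated on:** add one VAS reading at Visit 2 before anaesthesia, with the same scale and wording as the post-operative reading. Show it by arm in the baseline table. Analyse post-operative VAS by ANCOVA, with arm and pre-operative VAS as a continuous covariate, and name this in the Statistical Analysis Plan before arm-level outcomes are seen.

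**For patients already operated on:** the reading cannot be recovered. Pre-specify adjustment for the chronic-pain history, prior chronic opioid use and pre-operative analgesic use recorded at Visit 1. If enrolment is complete, this is the whole fix. If only some patients can have the baseline score, state in advance how the two groups enter one model.

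**Cost:** about a minute per patient, one form field and one model term, with no extra visit. The downside is that missing baseline scores need a simple rule, such as imputing the overall mean of the covariate without regard to arm.

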### Visit 3 (Day 14 to Day 30)

- In person post-operative follow-up assessment; (this will take an additional 15-30 min)- for standard of care and for research purposes;
- Collection of postoperative pathology reports, post-operative opioid use; (this will take an additional 30-45 min) – for standard of care and for research purposes;

Adverse events will be monitored and collected through the Day 30 visit, to include the following categories: Death, Life-threatening, Hospitalization (initial prolonged), Disability or Permanent Damage, Required Intervention to Prevent Permanent Impairment or Damage

(Devices), Other Serious (Important Medical Events). This will be accomplished through assessment of all body systems, with specific focus on: respiratory: decreased respirations, shallow breathing, decreased SPO2; integumentary: swelling, pressure, or crackling sound skin on palpitation of skin, increased abdominal distension; neurological: uncontrolled pain.

For patients randomized to 12 mmHg, if the surgeon deems that the visualization is not adequate to safely operate, then they may elect to increase the pressure to the standard 15 mmHg to improve visualization.

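### Arm differences in pain medication prescribed, taken, and later opioid use may partly reflect prescribing rather than pain, because nothing keeps the prescriber unaware of the arm

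*Combined protocol and SAP*

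**What the plan says.** - **Protocol, Visit 2 (Day 1).** The post-operative assessment includes the VAS and "pain medication – prescribed and taken". The list is marked as serving both standard care and research.
- **Protocol, Visit 3 (Day 14 to Day 30).** A further item is "Collection of postoperative pathology reports, post-operative opioid use", marked the same way.
- **When the arm is assigned.** Visit 2 specifies "Post-anesthesia randomization to group A or group B". It does not say who is told the result.
- **What the surgeon knows.** The end of the Visit 3 section reads "For patients randomized to 12 mmHg, if the surgeon deems that the visualization is not adequate to safely operate", and then "they may elect to increase the pressure to the standard 15 mmHg to improve visualization". A surgeon can use this allowance only by knowing the arm.
- **Statistical Analysis Plan.** After announcing a table of characteristics by assigned group, it gives one rule for continuous variables (a t-test) and one for categorical variables (a chi-square test). It has no separate rule for the amount prescribed or taken.
- **Not stated.** The documents do not say who prescribes post-operative analgesia, whether anyone is blinded, whether orders are standardised, or which collected item is the primary outcome.

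**The concern.** The amount prescribed is a clinician's decision. The amount taken is the patient's response, but for prescribed drugs it is limited by supply. If whoever prescribes knows the arm and expects less pain at 12 mmHg, group B may be given less for the same pain. The sponsor does expect a lower score there: the SAP assumes 17 mm against 29 mm. Part of such a gap could pass into medication taken at Visit 2 and opioid use at Visit 3.

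A lower analgesic or opioid total in group B might then be reported as a benefit of lower pressure when it is partly a record of prescribing habits. Randomization after anaesthesia leaves time to record orders while the arm is still unknown, but the plan does not use it.

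**Working it through.** **Document figures.** The SAP gives means of 17 and 29 mm with SDs of 20 and 24 mm. Pooled SD = √((20² + 24²)/2) = 22.09 mm, and 12/22.09 = 0.543, which matches the stated effect size of 0.54. This calculation is in millimetres, which fits the VAS and not medication. The only input taken from it is the number evaluable: 50 × (1 − 0.10) = 45 per group. The SAP states no significance level or sidedness; two-sided 5% is assumed here.

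**Does the route exist?**
1. The surgeon knows the arm: shown by the Visit 3 allowance.
2. The prescriber knows the arm: not shown, since the prescriber is not identified, but nothing prevents it.
3. The amount prescribed can respond to that knowledge: possible, since no standard orders or prescribing rule are described.
4. The amount taken follows the amount prescribed: in part. It holds for prescribed drugs in patients who would use their whole supply.

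The route is open but not demonstrated.

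**Illustration 1: a shift in medication taken.** All inputs are assumed: group B is prescribed 5 fewer tablets, a fraction 0.2 to 0.5 of those would have been taken, and the SD of tablets taken is 8. There is no true difference in pain.

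Shift in SD units = 5 × fraction / 8. The chance of p < 0.05 comes from the noncentral t with 88 degrees of freedom and noncentrality shift × √(45/2).

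| Fraction | Shift (tablets) | Shift (SD) | Noncentrality | Chance of p < 0.05 |
|---|---|---|---|---|
| 0 | 0 | 0 | 0 | 5.0% |
| 0.20 | 1.0 | 0.125 | 0.59 | 9.0% |
| 0.35 | 1.75 | 0.219 | 1.04 | 17.7% |
| 0.50 | 2.5 | 0.3125 | 1.48 | 31.1% |

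**Illustration 2: a strict cap.** Analgesic need is drawn from the same gamma distribution in both arms (shape 1.5, scale 8, mean 12 units). The amount taken is the smaller of need and supply, with 45 per group and 4,000 simulated trials per setting.

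| Supply, A vs B | Mean difference in amount taken | Chance of p < 0.05 |
|---|---|---|
| 20 vs 20 | 0.0 | 5.0% |
| 20 vs 18 | 0.4 | 6.1% |
| 20 vs 15 | 1.1 | 14.3% |
| 20 vs 12 | 2.2 | 47.2% |

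With the same 5-unit gap as in the first illustration, the cap passes on 1.14/5 = 0.23 of the difference, near the lower end of the assumed 0.2 to 0.5. Both illustrations show that a prescribing gap can create a medication difference without a pain difference. Neither estimates how large a gap this trial will have.

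**The case against.** A reader might infer that medication is a trial outcome set by clinicians known to be unblinded, and that patients can take no more than those clinicians allow. The documents do not support that reading.

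- **Prescriber.** Only the operating surgeon's knowledge can be shown. Ward, recovery or discharge prescribers are not mentioned. This stands, and the point can say only that prescribing may be affected.
- **Status of the item.** Medication sits in a collection list with blood loss, pathology and length of stay. No section calls it an outcome, and the sizing in mm points to the VAS. The t-test sentence follows a sentence about a table of characteristics, so applying it to medication is one reading. This stands and limits the severity. But no outcome hierarchy is given, the items are collected partly for research, and the SAP offers no other rule for them.
- **The cap.** Non-prescription analgesics and further prescriptions before Visit 3 are not excluded, so the limit is loose. This stands.
- **Visibility.** The VAS, amount prescribed and amount taken are recorded together, so a prescribing difference without a VAS difference could be seen. This stands as far as it goes, but the plan does not say they will be reported together, and the VAS is listed only at Visit 2.
- **Magnitude.** Every input except the 45 per group is assumed, and the 9% lower end already presupposes biased prescribing. This stands; the figures are illustration only.
- **Remedy.** Orders can still be changed after surgery by someone who knows the arm, and testing only the amount taken would not cure the problem, because that amount can itself depend on what was prescribed. Both stand. Recording orders early reduces the bias, and the log makes what remains visible.

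**Conclusion.** The concern holds in limited form. The operating surgeon knows the arm, and the documents neither keep whoever prescribes unaware of it nor standardise orders. A difference between arms in medication prescribed, medication taken or later opioid use may therefore partly reflect prescribing, and the plan has no safeguard and no rule for reading such a result.

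The documents do not establish that the bias will occur, who would introduce it, or how large it would be. The 9% to 31% range depends on a shift of 0.125 to 0.31 SD, 45 evaluable patients per group and a two-sided 5% test. With no shift the error stays at 5%. A reader might take that range as the false-positive rate of this trial; it is not. The point does not challenge the VAS comparison or the sample size.

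**What to change.** **Protocol, Visit 2.** Add a sentence: where practicable, the team records its usual post-operative analgesic orders before the allocation is opened. The content of the orders, and any later change, remain wholly the team's decision. Each change is logged with its reason.

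**Statistical Analysis Plan.** Add that medication prescribed will be reported by arm as description, without a test. Medication taken and post-operative opioid use will be shown beside the amount prescribed and the VAS. State in advance that a medication difference without a VAS difference will not be read as evidence of less pain.

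**Cost.** A short addition to each section, plus a log entry whenever an order is changed after surgery. Some orders will be changed, so the bias is reduced and made visible but not removed. The SAP describes randomization in the past tense; if enrolment has begun, the SAP addition can still be made before the data are analysed.

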### Visit 3 (Day 14 to Day 30)

- In person post-operative follow-up assessment; (this will take an additional 15-30 min)- for standard of care and for research purposes;
- Collection of postoperative pathology reports, post-operative opioid use; (this will take an additional 30-45 min) – for standard of care and for research purposes;

Adverse events will be monitored and collected through the Day 30 visit, to include the following categories: Death, Life-threatening, Hospitalization (initial prolonged), Disability or Permanent Damage, Required Intervention to Prevent Permanent Impairment or Damage

(Devices), Other Serious (Important Medical Events). This will be accomplished through assessment of all body systems, with specific focus on: respiratory: decreased respirations, shallow breathing, decreased SPO2; integumentary: swelling, pressure, or crackling sound skin on palpitation of skin, increased abdominal distension; neurological: uncontrolled pain.

For patients randomized to 12 mmHg, if the surgeon deems that the visualization is not adequate to safely operate, then they may elect to increase the pressure to the standard 15 mmHg to improve visualization.

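### Does permitting group B patients to be raised to 15 mmHg during surgery undermine the planned comparison or its sample size?

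*Combined protocol and SAP*

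**What the plan says.** The conversion rule closes the protocol section headed Visit 3 (Day 14 to Day 30). For a patient randomised to 12 mmHg whose view is inadequate, the surgeon decides, and "then they may elect to increase the pressure to the standard 15 mmHg to improve visualization". No movement from 15 to 12 mmHg is described, so conversion runs one way. The Visit 2 (Day 1) section lists "adjustment of intra-operative insufflation pressure" among the procedures. The opening Study Protocol section notes that "for patients with extreme upper BMIs, visualization can be more challenging", admits patients up to a BMI of 55.0, and does not tie randomisation to BMI.

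The Statistical Analysis Plan sizes the trial on "estimated means of 17mm for the experimental arm (SD 20mm) and 29mm for the control arm (SD 24mm"), with an "anticipated effect size of 0.54", and arrives at a "necessary sample size of 50 participants per group (100 total"). The only allowance it names is 10% loss to follow-up. Its second paragraph sets out the characteristics table by the arm each patient was assigned. The next two sentences give summaries and tests, with means and standard deviations reported for each group. No sentence deals with patients whose pressure was raised.

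**The concern.** A patient converted to 15 mmHg has received some of the control treatment. Kept in group B, such patients pull that arm's mean pain towards the control mean, so the observed difference may fall short of 12 mm and power may fall with it. The sample size shows no margin for this.

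The handling question looks more serious. Converted patients are unlikely to be a random subset, because the protocol itself links difficult visualisation to very high BMI. Moving them to group A or leaving them out would make the arms differ in more than assigned pressure. Since the assigned-arm wording is attached to the characteristics table and not repeated for the tests, an analyst might seem free to choose among three handlings, only one of which preserves the randomised comparison.

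**Working it through.** **Inputs from the Statistical Analysis Plan.** Means 17 and 29 mm, SDs 20 and 24 mm, 50 per group, 10% loss (50 × 0.9 = 45 evaluable per group), t-test.

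**Not in the documents, so assumed.** Conversion share c (5%, 10%, 20% tried), significance level 5%, one- and two-sided, pain level in converted patients.

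**The plan's own figures.**
- Pooled SD = √((20² + 24²)/2) = √488 = 22.09 mm.
- Effect size = (29 − 17)/22.09 = 0.543, which matches the stated 0.54.
- One-sided 5%, 80% power: 43 to 44 per group at 0.54, and 48 to 49 after dividing by 0.9. This is within 2 of the stated 50.
- Two-sided 5%, 80% power: 54 to 55 per group, and 60 to 62 after dividing by 0.9. This does not give 50.

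**Worst-case dilution.** Suppose 17 mm applies only to patients kept at 12 mmHg and converted patients have the full control distribution. Then:
- mean of B = 17(1 − c) + 29c, so the difference is 12(1 − c);
- variance of B = 400(1 − c) + 576c + 144c(1 − c);
- effect size = 12(1 − c)/√((variance of B + 576)/2).

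At c = 0.10 the difference is 12 × 0.9 = 10.8 mm. The variance of B is 360 + 57.6 + 12.96 = 430.56. The pooled SD is √((430.56 + 576)/2) = 22.43, and the effect size is 10.8/22.43 = 0.48.

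Power from the noncentral t distribution, 45 per group:

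| Conversion (assumed) | Difference, mm | Effect size | Two-sided 5% | One-sided 5% |
|---|---|---|---|---|
| 0% | 12.0 | 0.54 | 72% | 82% |
| 5% | 11.4 | 0.51 | 67% | 78% |
| 10% | 10.8 | 0.48 | 62% | 73% |
| 20% | 9.6 | 0.42 | 51% | 63% |

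From 80% down to 62% (10% conversion, two-sided) is 18 points. Of these, 80 − 72 = 8 are already missing with no conversion and come from the unstated sidedness. The other 10 depend on the two assumptions above.

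**Milder dilution.** A patient raised part-way has had some time at 12 mmHg. If converted patients keep half the benefit, 10% conversion gives 12 − 0.10 × 6 = 11.4 mm. Power is then about 67% two-sided or 78% one-sided, a loss of 4 to 5 points.

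**Would a complier-average estimate help?** It divides the assigned-arm difference by the share kept at 12 mmHg, and is correct only if assignment has no effect on pain in converted patients. If they keep half the benefit:
- at 10% conversion, 11.4/0.9 = 12.7 mm;
- at 20% conversion, (12 − 0.20 × 6)/0.8 = 10.8/0.8 = 13.5 mm.

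Both overstate the true 12 mm.

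**The case for a change.** The best case for a change is that the Statistical Analysis Plan leaves the handling open, at most 100 patients are involved, and one sentence would close it before outcomes are compared. Even on the one-sided reading that comes close to 50 per group, 5% conversion with full control-level pain takes power from 82% to 78%, below 80%.

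It stands that the plan gives no conversion rate, no margin for conversion and no explicit handling rule. The arithmetic is also right under its assumptions.

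The rest is weaker:
- The plan gives 17 mm for the experimental arm, without saying that this means patients kept at 12 mmHg. If the figure already reflects an arm with some conversions, there is nothing further to subtract.
- The sentence on tests follows directly on the one that defines the groups by assignment. The ordinary reading is that the same groups are meant. No text suggests excluding or reclassifying anyone.
- Bias in favour of 12 mmHg from dropping or moving converted patients needs those patients to have more postoperative pain than others. The documents link very high BMI to visualisation, not to pain.

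**Conclusion.** No change follows. Read in the ordinary way, the plan compares arms as assigned, with converted patients staying in group B. That comparison is unbiased for the effect of a policy of starting at 12 mmHg with conversion allowed, which is how the protocol says group B will be treated. Conversion can make the effect smaller and harder to detect, but it does not invalidate the test.

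The possible loss cannot be sized from the documents. It is nil if 17 mm already includes conversions. At an assumed 10% rate it is 4 to 5 points of power if converted patients keep half the benefit. If they keep none, it is 10 points two-sided (72% to 62%) or 9 one-sided (82% to 73%).

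Restating power at a chosen rate would put an invented figure in the plan and correct none that it states. A complier-average estimate would only be supplementary, and could overstate the benefit. Writing out the assigned-arm rule would be tidy, but it would only confirm what an analyst would already do. The conclusion would differ if any text called for excluding or moving converted patients; none does.

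### Does allowing group B to be raised from 12 to 15 mmHg contradict the stated pressures, or leave the result uninterpretable?

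*Combined protocol and SAP*

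**What the plan says.** All references are to the combined protocol and SAP.

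- **Study Protocol:** "Insufflation pressures of either 12 mmHg (group B) or 15 mmHg (group A) will be used for this research, regardless of the subject's BMI". The same paragraph concedes that "for patients with extreme upper BMIs, visualization can be more challenging", sets the upper BMI limit at 55.0, states that "BMI will be one of the data points recorded for patients", and adds that randomization does not depend on BMI.
- **Visit 2 (Day 1):** the bullet describing insufflation at the assigned pressure also lists "adjustment of intra-operative insufflation pressure". A separate bullet lists the data: "Post-operative assessment to include the procedure details: indication for procedure, length, estimated blood loss, surgical complications", followed by pathology, VAS, pain medication and length of stay.
- **Visit 3 (Day 14 to Day 30), last paragraph:** for patients randomized to 12 mmHg, surgeons who find the view inadequate for safe operating are told "they may elect to increase the pressure to the standard 15 mmHg to improve visualization".
- **Statistical Analysis Plan:** "We will provide a table of demographic and clinical characteristics by assigned group", then t-tests for continuous variables and chi-square tests for categorical ones. Converted patients are not mentioned.

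**The concern.** The Study Protocol sentence carries no exception, and the Visit 3 paragraph supplies one. The protocol itself ties difficult views to very high BMI. Allocation is therefore independent of BMI, while the pressure delivered in group B may not be. The one explicit switching rule runs in a single direction, towards the control arm's pressure.

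The data lists for the three visits include BMI but have no named item for final pressure or conversion.

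Two things would be at stake. The first is what the result may be called: 12 versus 15 mmHg, or a policy of starting at 12 and raising when needed. The second is how to read a small difference. Without a count of conversions, it could mean that 12 mmHg helps little or that many patients did not stay at 12 mmHg.

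**Working it through.** **1. Setting the passages side by side.** The Study Protocol sentence is about BMI, and the paragraph goes on to say that randomization does not depend on BMI. Its plain sense is that pressure is not chosen by body size. The Visit 3 exception is triggered by the surgeon's view of the field, not by BMI, and it is addressed to patients already randomized to 12 mmHg. Visit 2 puts assigned insufflation and pressure adjustment in one bullet. Together these describe an assigned pressure with one stated exception. The sentences are in tension, but they can all hold at once.

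**2. Reproducing the plan's figures.** Inputs from the Statistical Analysis Plan: means 17 mm (SD 20) and 29 mm (SD 24), effect size 0.54, 50 per group, 10% loss.

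- Pooled SD = √((20² + 24²)/2) = √488 = 22.09. Effect size = 12/22.09 = 0.543, which agrees with 0.54.
- The plan does not state alpha, sidedness or power. At one-sided 5% and 80% power, the normal formula with 0.54 gives 43 per group, and 43/0.9 rounds up to 48, close to 50. The two-sided version gives 54, or 60 after loss.
- Evaluable patients: 50 × 0.9 = 45 per group.

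**3. How far conversions could dilute the difference.** The documents give no conversion rate *c*, so 5, 10 and 20% are assumptions. Converted patients are assumed either to have the control mean (difference = 12(1 − *c*)) or to keep half the benefit (difference = 12(1 − *c*/2)).

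| *c* | Control mean | Half benefit | Shrinkage |
|---|---|---|---|
| 5% | 11.4 mm | 11.7 mm | 0.3 to 0.6 mm |
| 10% | 10.8 mm | 11.4 mm | 0.6 to 1.2 mm |
| 20% | 9.6 mm | 10.8 mm | 1.2 to 2.4 mm |

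Under the control-mean assumption, with converts also having SD 24, the variance in group B is (1 − *c*)·400 + *c*·576 + *c*(1 − *c*)·144. The effect size is then 0.512, 0.481 and 0.422 at the three rates. With 45 per group, two-sided 5% power from the noncentral t falls from 0.722 with no conversions to 0.671, 0.617 and 0.508. One-sided power falls from 0.819 to 0.778, 0.733 and 0.634. If the 17 mm planning mean already reflects some conversions at that rate, the extra loss is nil; the plan does not say.

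**4. What a recorded count would settle.** The standard error of the difference is √((400 + 576)/45) = 4.66 mm. With a t multiplier of 1.987 on 88 degrees of freedom, the half-width is 9.3 mm.

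Suppose the trial observes 10.8 mm, so the interval is 1.5 to 20.1 mm. If 10% are known to have converted, the benefit at a maintained 12 mmHg would be 10.8/0.90 = 12.0 mm if converts lose it all, or 10.8/0.95 = 11.4 mm if they keep half. With no conversions it is 10.8 mm. These answers span 1.2 mm, inside an interval 18.6 mm wide. The count also cannot say which assumption about converts is right.

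**The case for a change.** The best case for a change is that it costs almost nothing and may be impossible to make good later. If the final pressure is not written down in theatre, nobody can reconstruct it, and a reader of the report cannot tell how often the experimental condition was maintained. Pressure adjustment appears in the bullet describing what is done, not in the bullet listing what is collected. On wording, the randomization clause is separate from the sentence saying which pressures are used, so the unqualified reading is available too.

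Part of this stands. Recording of delivered pressure is not explicit, and a report that gives the number converted is better than one that does not. But the data list is introduced as a set of inclusions and need not be exhaustive, and adjustment of pressure is a named Visit 2 item. It would be too strong to say the plan leaves the matter out. Nor is it certain that only group B's pressure can move, since the Visit 2 item is not limited to one group.

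The power losses do not strengthen the case. They rest wholly on assumed conversion rates and outcomes for converts, and recording conversions would recover none of the lost power. A breakdown of BMI by conversion would be thin: at 10% of 50 it would describe five patients.

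**Conclusion.** No change to the plan follows. The Study Protocol, Visit 2 and Visit 3 passages can be read together as an assigned pressure, not tailored to BMI, with a stated exception when the view is inadequate. No view is taken here on which pressure or switching rule is right.

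The primary inference is not at risk. Comparing patients as randomized is valid whatever pressure they ended on, and it answers the question of assigning 12 mmHg with that exception available. The SAP ties assigned group to the characteristics table, and carrying it through to the outcome comparisons is the natural reading.

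The possible shrinkage is 0.3 to 2.4 mm at assumed conversion rates of 5 to 20%, small beside the ±9.3 mm precision of the trial, and nil if the planning mean already allows for conversions. What is left is missing detail: a field for delivered pressure, and a count in the report. An analyst would be expected to supply both from an adjustment already listed at Visit 2. That expectation is an assumption, since the documents do not say the value is stored. No stated rule or number gives a wrong result without it.
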